## 4. PATIENT SELECTION

### 4.1. Diagnosis and inclusion criteria

To be eligible, patients must meet all of the following criteria:

1. Signed a written informed consent form prior to any trial specific procedures.

**Note:** *If the patient is physically unable to provide their written consent, a trusted person of their choice, independent of the Investigator or the Sponsor, can confirm the patients consent in writing.*

2. Men with histologically or cytologically confirmed adenocarcinoma of the prostate.
3. Aged  $\geq 18$  years old at the time of signing informed consent
4. *De novo* metastatic disease defined by clinical or radiographic evidence of metastases.

**Note:** *For patients with nodal metastases only, only patients with extra-pelvic enlarged lymph nodes (lymph nodes located above the iliac bifurcation) can be included if they have either:*

- *At least one extra-pelvic lymph node  $\geq 2$  cm*
  - *At least one extra-pelvic lymph node  $\geq 1$  cm if the patients also have at least one pelvic lymph node  $\geq 2$  cm*
5. Measurable disease or bone lesions that are evaluable according to PCWG3 criteria ([Scher, 2016](#); Appendix 3).
  6. Ineligible for treatment with all of the following drugs: docetaxel, abiraterone, enzalutamide, apalutamide; AND meets at least one of the following frailty criteria:
    - Activities of daily living (ADL) assessment (excluding urinary incontinence question) score 3 or 4/5 ([Katz, 1970](#); Appendix 8), or;
    - 4-Instrumental activities of daily living (4-IADL) assessment score 2 or 3/4 (Lawton, 1969; Appendix 8), or;
    - A Grade 3 event on the Cumulative Illness Score Rating-Geriatrics (CISR-G) questionnaire ([Miller, 1992](#); Appendix 9), or;
    - Body mass index (BMI)  $\leq 21$  kg/m^2 and/or  $>5\%$  weight loss in the last 6 months, or;
    - Timed up and go test (TUG)  $> 14$  sec ([Podsiadlo, 1991](#); Appendix 8).

*Nota Bene: Regarding CISR-G assessment, more specifically genitourinary scoring, score N°4 is not applicable*

7. Adequate bone marrow function: haemoglobin  $\geq 80\text{g/L}$ , white blood cells  $\geq 3.0 \times 10^9/\text{L}$  and platelets  $\geq 80 \times 10^9/\text{L}$ .
8. Adequate liver function: alanine aminotransferase (ALT)  $< 2 \times \text{ULN}$  and bilirubin  $< 1.5 \times \text{ULN}$ , (or if bilirubin is between 1.5-2x ULN, they must have a normal conjugated bilirubin). For patients with documented liver metastasis ALT  $< 5 \times \text{ULN}$  is acceptable
9. Adequate renal function: calculated creatinine clearance  $> 30 \text{ ml/min}$  (using the MDRD or CKD EPI method)
10. For sexually active men, agreement to use adequate contraception for the duration of trial participation and up to 2 weeks after completing study treatment
11. Affiliated to the social security system or in possession of equivalent private health insurance (according to local regulations for participation in clinical trials)
12. Willing and able to comply with the protocol for the duration of the trial including undergoing treatment and scheduled visits, and examinations including follow-up.

#### 4.2. Non-inclusion criteria

Patients are not eligible to participate in the trial if they meet any of the following criteria:

1. Three or more Grade 3, or any Grade 4 events on the CISR-G questionnaire.

*Nota Bene: Regarding CISR-G assessment, more specifically genitourinary scoring, score N°4 is not applicable*

2. Eastern Cooperative Oncology Group (ECOG) performance status score  $\geq 3$  (Appendix 5).
3. Hypertension not controlled by an anti-hypertensive treatment (systolic blood pressure [BP]  $\geq 160 \text{ mmHg}$  or diastolic BP  $\geq 95 \text{ mmHg}$ ; 3 consecutive measures taken 5 minutes apart).
4. Acute toxicities of prior treatments and procedures not resolved to grade  $\leq 1$  or baseline before randomisation with the exception of hot flushes and erectile dysfunction.
5. Previous systemic treatment for prostate cancer, except less than 12 weeks of ADT and/or an old-generation AR inhibitor.
6. Severe or uncontrolled concurrent disease, infection or co-morbidity.
7. Known hypersensitivity to the study treatment or any of its ingredients.
8. Major surgery within 28 days before randomisation.
9. Any of the following within 6 months before randomisation: stroke, myocardial infarction, severe/unstable angina pectoris, coronary/peripheral artery bypass graft; congestive heart failure New York Heart Association (NYHA) Class III or IV.
10. Prior malignancy  $\leq 3$  years before study enrolment. Adequately treated basal cell or squamous cell carcinoma of skin or superficial bladder cancer that has not spread behind the

connective tissue layer (i.e., pTis, pTa, and pT1) is allowed, as well as any localized cancer for which treatment has been completed  $\geq 6$  months before randomisation and from which the subject has been disease-free, or for which the risk of relapse is less than 30%, as well as early stage chronic lymphocytic leukaemia that does not require any specific treatment.

11. Inability to swallow oral medications
12. Gastrointestinal disorder or procedure that can be expected to interfere significantly with the absorption of study treatment.
13. Known to have active viral hepatitis, active human immunodeficiency virus (HIV) or chronic liver disease at screening.
14. Treatment with any investigational product within 28 days before randomisation.
15. Concurrent participation in another clinical trial involving an investigational product (patients enrolled in non-experimental trials with no modification of the standard of care can be included).
16. Individual of full age deprived of liberty or placed under a legal protection measure (tutorship/curatorship/temporary guardianship).
17. Significantly altered mental status prohibiting the understanding of the study or with psychological, familial, sociological or geographical condition potentially hampering compliance with the study protocol and follow-up schedule or any condition that, in the opinion of the investigator, would preclude participation in this trial.

## 5. TRIAL TREATMENTS/INTERVENTIONS

### 5.1. Description of trial treatments/interventions

Patients who have signed the informed consent form and are eligible for inclusion will be randomised to receive the following treatments:

- Experimental arm: ADT + darolutamide 600 mg po b.i.d.
- Control arm: ADT + placebo po b.i.d.

#### Androgen-deprivation therapy

All patients will receive continuous ADT. Intermittent ADT will not be used in this trial, except if severe intolerance to ADT occurs.

The choice of ADT is left to the discretion of the investigator, to be administered according to local standard procedures but should consist in either:

- A bilateral orchiectomy
- A luteinizing hormone-releasing hormone (LHRH) agonists associated, during the first weeks, with an androgen receptor (AR) inhibitor (e.g. bicalutamide or flutamine). All formulations of LHRH agonists (monthly, 3 monthly, 6 monthly, etc) are acceptable as long as treatment is used continuously.

**Note:** *If the patient has been receiving LHRH + AR inhibitor for more than 4 weeks prior to randomisation, the androgen receptor inhibitor should be discontinued at randomization.*

- A LHRH antagonist.

Patients may have initiated ADT therapy up to 12 weeks prior to randomization.

### **Darolutamide/placebo**

Patients are to take two 300 mg tablets of darolutamide or placebo twice daily, (i.e equivalent to a total daily dose of 1200 mg) with food and a glass of water. This dose may be adjusted in the event of adverse toxicity (see Section 5.5).

Treatment observance will be recorded in the eCRF, and the patients will be asked to complete a personal logbook daily.

## **5.2. Acquisition, reception, and storage**

The investigational product (IP) darolutamide and placebo control will be provided by the sponsor. It will be distributed to the pharmacy at the investigational site via a dedicated courier (Eurofins) in accordance with the current Good Distribution Practices guidelines.

The pharmacist of the trial site will receive numbered treatment and will acknowledge receipt of all deliveries by sending the necessary completed documents to the distributor.

The pharmacist is responsible for a safe and proper handling and storage of the IP at the investigational site. The IP must be stored in a locked facility with access restricted to the pharmacist and authorized personnel, and under environmental conditions consistent with the drug manufacturer recommendations (Investigator's Brochure).

- Darolutamide and placebo must be stored below 30°C.

Up to date temperature logs must be maintained by the pharmacist/investigator to document adequate storage during the trial. These logs must be available at the site during monitoring visits, and in the event of an audit or inspection.

If the storage conditions as indicated above are exceeded (e.g. temperature excursion), the pharmacist/investigator must place the corresponding treatments in quarantine and immediately notify the sponsor who will indicate the procedure to follow. Under no circumstances should these treatments be delivered to trial patients without prior authorization by the sponsor.

## **5.3. Trial treatments accountability, return and destruction**

Patients will return unused and used treatments to the physician-investigator or to the pharmacy. The pharmacist (or investigator) of each investigational site will count the returned tablets and accurately keep record of them. These records will be made available to the clinical research associate (CRA) mandated by the sponsor.

The investigator/pharmacist must ensure that the IP is administrated only to patients randomised in this trial. The IP must not to be used outside the context of the trial protocol.

The pharmacist or authorized staff must document the receipt, dispensation, return and destruction of all IP received during this trial. Records of IP delivery to the site, the inventory at the site, the use by each patient, and the return to the sponsor or destruction by the site must be implemented and maintained by the pharmacist or another appropriately trained individual at the investigational site. The following minimum information must be present: all relevant dates (delivery dates, dispensation, returns, and destruction), quantities, and IP batch numbers. Accountability form will be provided by the sponsor to ensure trial treatment accountability.

The pharmacist will implement an accounting of IP dispensed, used, unused, returned by the patients. The accountability of the IP returned by patients will be systematically done by the pharmacist of the site.

This process will be monitored by the Unicancer CRA during the trial. The CRA will check that the accountability documentation has been filled in and signed by the pharmacist before the IP, used and unused, are destroyed.

All remaining IP, used and unused, shall be collected and returned for destruction. The destruction will take place at the investigator sites under the responsibility of their pharmacist in accordance with national regulatory requirements, and with prior formal agreement from the sponsor. A certificate of destruction, identifying the numbered products concerned, will be provided to the sponsor.

#### 5.4. Formulation, appearance, packaging, and labelling

Darolutamide and the placebo control are formulated as blue film-coated immediate-release 0.3 g tablet for oral application.

The tablets are provided in a high-density polyethylene white opaque plastic bottle.

The darolutamide and placebo control will be provided by the Sponsor and labelled appropriately as IP for this study in accordance with the specific requirements of this study, applicable Good Manufacturing Practices, and national regulations.

Packaging will be performed by Bayer. Relabelling will be performed by Eurofins.

#### 5.5. Dose adaptation

##### **General requirements for dose modifications**

A patient who experiences a Grade 3 or 4 AE that is considered related to the study drug (darolutamide/placebo), should interrupt the study drug until the AE improves to Grade  $\leq 2$  or to baseline status. Specific guidance on how to proceed in the setting of Grade 3-4 AEs is provided in Table 1 Study drug dose modifications for all AEs except for increases in ALT/AST” and Table 2 Study drug dose modifications for increases in ALT and/or AST” .

##### **5.5.1. Study drug dose modifications for all AEs except for increases in ALT/AST**

**Table 1 Study drug dose modifications for all AEs except for increases in ALT/AST**

Severity grade (NCI-CTCAE v5.0)	Dose modifications	Study treatment withdrawal
Grade 0 – 2	Treat on time Per investigator’s decision to interrupt or reduce study drug a,b	Not applicable
Grade 3 – 4	Interrupt until Grade $\leq 2$ or baseline a ,	If Grade $\geq 3$ study drug-related AE occurs while the participant is on a

	When the severity is Grade $\leq 2$ , restart at a reduced dose 300 mg b.i.d b,c	dose of 300 mg b.i.d (following temporary or permanent dose reduction), the participant must be withdrawn from treatment with study drug
--	---	--

Excludes clinically non-significant and asymptomatic laboratory abnormalities

AE = Adverse Event; ALT = Alanine aminotransferase; AST = Aspartate aminotransferase; b.i.d = Twice daily; NCI-CTCAE v5.0 = National Cancer Institute Common Terminology Criteria for Adverse Events version 5.0;

a: If there is no recovery after 28 consecutive days, treatment with study drug should be permanently discontinued.

b: when AE returns to baseline or is resolved, re-escalation to 600 mg b.i.d may be considered by the investigator.

c: If, following a re-escalation to 600 mg b.i.d, a second Grade  $\geq 3$  study drug-related AE occurs, a permanent dose reduction to 300 mg b.i.d is required. A third occurrence of a Grade  $\geq 3$  study drug-related AE requires permanent discontinuation of treatment with study drug.

In the event of treatment interruption due to toxicity of more than 56 days, the decision to restart treatment or not should be discussed and agreed between the Investigator and Sponsor.

Dose reduction below 300 mg b.i.d is not recommended because efficacy has not been established. The maximum efficacious daily dose is the recommended dose of 600 mg b.i.d.

### 5.5.2. Study drug dose modifications for increases in ALT and/or AST

Cases of idiosyncratic Drug-Induced Liver Injury (DILI) with increases in ALT and/or AST to  $\geq 5$  and  $\geq 20 \times$  ULN, including with concomitant bilirubin elevation  $> 2 \times$  ULN, have been reported with darolutamide.

Liver function test (LFT) abnormalities were reversible upon darolutamide discontinuation. Participants who experience hepatic transaminase elevations suggestive of idiosyncratic DILI considered to be causally related to study drug, should discontinue study drug.

Additional laboratory tests monitoring is recommended for Grade  $\geq 2$  ALT and/or AST increase (ALT/AST  $> 3 \times$  ULN) as show in Table 2

**Table 2 Study drug dose modifications for increases in ALT and/or AST**

Severity grade (NCI CTCAE v.5.0)	ALT/AST increase
Grade 0 – 1	
 
- Treat on time.
 
- Per investigator's decision to interrupt or reduce study druga
 

Grade 2 - 4	
If ALT or AST rise to <math>> 3</math> ULN:
 
 
- Per investigator's decision to interrupt or reduce study drug,
 

	
 
- Monitor LFT (ALT, AST, total and direct bilirubin, ALP) and INR within 72 hours after the onset and then as frequently as needed according to investigator's clinical judgment, until ALT and/or AST returns to baseline or normal values.
 
- Participants must be discontinued from the study treatment in case of hepatic transaminase elevations suggestive of idiosyncratic DILI considered to be causally related to study drug. DILI should be suspected after other causes of liver injury, have been excluded. A further guidance for diagnostic and laboratory evaluation for suspected DILI, is provided in Appendix 14
 
- The criteria for darolutamide discontinuation (FDA 2009) are: 
 
o ALT or AST > 8xULN
 
o ALT or AST > 5xULN for more than 2 weeks
 
o ALT or AST > 3xULN and (TBL > 2xULN or INR > 1.5)
 
o ALT or AST > 3xULN with the appearance of fatigue, nausea, vomiting, right upper quadrant pain or tenderness, fever, rash, and/or eosinophilia (> 5%).
 
 
 

For all grades:	
Further recommendations:
 
 
- If ALT and AST return to normal values or to baseline after study drug interruption, study drug may be restarted at the reduced dose of 300 mg b.i.d.
 
- If, at the reduced dose, there is no increase of ALT or AST in the subsequent 2 weeks, full dose may be resumed.
 
- If, at the reduced or full dose, ALT or AST values rise again, study drug should be permanently discontinued. Monitor LFTs until ALT and/or AST return to baseline or normal values.
 

AE = Adverse Event; ALP = Alkaline phosphatase; ALT = Alanine aminotransferase; AST = Aspartate aminotransferase; b.i.d = Twice daily; DILI = Drug-Induced Liver Injury; INR = International Normalised Ratio; LFT = Liver Function Test; NCI-CTCAE v5.0 = National Cancer Institute Common Terminology Criteria for Adverse Events version 5.0; TBL = Total Bilirubin; ULN = Upper Limit of Normal

a : If there is no recovery after 28 consecutive days, treatment with study drug would be permanently discontinued.

If the patient discontinues darolutamide/placebo due to toxicity, ADT should be continued.

If the patient experiences intolerable side effects due to ADT then the ADT may be substituted with another ADT at the discretion of the investigator. If the patient refuses the ADT, the investigator will ask the sponsor what steps to take.

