#### **2- Study drug dose modifications for increases in ALT and/or AST**

Cases of idiosyncratic Drug-Induced Liver Injury (DILI) with increases in ALT and/or AST to  $\geq 5$  and  $\geq 20$ x ULN, including with concomitant bilirubin elevation  $> 2$ x ULN, have been reported with darolutamide.

Liver function test (LFT) abnormalities were reversible upon darolutamide discontinuation.

In case of hepatic transaminase elevations suggestive of idiosyncratic Drug Induced Liver Injury (DILI) considered to be causally related to darolutamide, treatment with darolutamide should be permanently discontinued. More specific guidance on how to proceed in the case of DILI is provided in the protocol in section 5.5 dose adaptation.

In the event of treatment interruption due to toxicity of more than 56 days, the decision to restart treatment or not should be discussed and agreed between the Investigator and Sponsor.

Dose reduction below 300 mg b.i.d. is not recommended, because efficacy has not been established.

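### The hepatic dose rules give two different instructions for a related Grade 3–4 ALT/AST rise, and leave open whether a stop under the listed criteria is permanent

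*Protocol*

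**What the plan says.** Four parts of the protocol govern the same event.

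- **General rule** (Protocol Summary, Dose modification; repeated in Section 5.5): "A patient who experiences a Grade 3 or 4 AE that is considered related to the study drug (darolutamide/placebo), should interrupt the study drug". The interruption lasts until the event is Grade 2 or lower, or back to baseline. ALT and AST are not exempted. Section 5.5 adds that "Specific guidance on how to proceed in the setting of Grade 3-4 AEs is provided in Table 1" and goes on to name Table 2 as well.
- **Table 2, Grade 2–4 row** (Section 5.5.2): above 3 × ULN, the action is "Per investigator's decision to interrupt or reduce study drug". The same cell requires discontinuation for rises suggestive of drug-related idiosyncratic liver injury (DILI). It then gives a list introduced by "The criteria for darolutamide discontinuation (FDA 2009) are": above 8 × ULN; above 5 × ULN for more than 2 weeks; above 3 × ULN with raised bilirubin or INR; above 3 × ULN with listed symptoms or eosinophilia.
- **Table 2, all-grades row**: once ALT and AST are normal or at baseline after an interruption, "study drug may be restarted at the reduced dose of 300 mg b.i.d". Full dose may follow if neither rises over the next 2 weeks. "If, at the reduced or full dose, ALT or AST values rise again, study drug should be permanently discontinued".
- **Protocol Summary, item 2 on ALT/AST**: for related DILI, "treatment with darolutamide should be permanently discontinued".

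A footnote to Table 2 adds a permanent stop if there is no recovery after 28 days.

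**The concern.** A dose-modification table has to give one answer for one patient. Here the general rule and the table that is meant to detail it differ on whether a reduced dose may be continued through a related Grade 3–4 transaminase rise. The table also leaves unclear how its discontinuation list relates to its restart row.

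The stakes are mainly safety. The protocol itself reports cases with ALT or AST at 20 × ULN or more and concomitant bilirubin elevation, and the population is selected for frailty. About 100 sites have to apply the text. If they read it differently, reasons for discontinuation, dose reductions and exposure, which Section 10.3.3 summarises under a key secondary safety objective, will partly reflect site interpretation.

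**Working it through.** The plan gives no figure to reproduce on this point. The check is to apply every rule to defined patients.

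**Patient A: related Grade 3 rise, no listed criterion met, not judged suggestive of DILI.**

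One assumption is needed. For transaminases the protocol prints only one grade boundary: Section 5.5.2 equates Grade 2 or higher with more than 3 × ULN. Patient A exists if Grade 3 begins anywhere between 3 and 8 × ULN. If it began above 8 × ULN, every Grade 3–4 rise would already meet a criterion and this first conflict would be empty.

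| Rule | Instruction for patient A |
|---|---|
| Summary and Section 5.5, general rule | Should interrupt |
| Table 1 | Not applicable: its title excludes ALT/AST increases |
| Table 2, Grade 2–4 row | Interrupt or only reduce, at the investigator's choice |
| Table 2, discontinuation list | Not met |

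Reducing without interrupting is allowed by the third line and not by the first. No sentence says which prevails.

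**Recovery level.** Suppose patient A had a normal baseline, was interrupted, and has fallen to Grade 2. By Section 5.5.2 the value is still above 3 × ULN. Under the general rule ("should interrupt the study drug until the AE improves to Grade" 2 or lower, or baseline) the interruption may end. Under Table 2 restart is not yet open, because it needs normal or baseline values.

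**Patient B: ALT above 8 × ULN, returning to baseline once study drug is stopped.** The discontinuation list applies. Whether that stop is permanent depends on which sentence is read:

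| Place | Called permanent? |
|---|---|
| Summary, related DILI | Yes |
| Section 5.5.2 text, related DILI | No |
| Table 2, DILI bullet | No |
| Table 2, discontinuation list | No |
| Table 2, renewed rise | Yes |
| Table 2, 28-day footnote | Yes |

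Three of six places carry the word; the list itself does not. Nor does the list say whether its criteria stand alone or only help to define DILI. The restart row covers all grades and is conditioned on a preceding interruption. It neither includes nor excludes patient B.

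**Secondary points.**

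1. *The 2-week condition.* Table 2 monitoring may end when values are back to baseline or normal, which is also when restart opens. No test is tied to the decision 2 weeks later. Scheduled chemistry is at days 30, 60, 120, 180 and 240, then every 120 days to 2 years and every 180 days after. The intervals are 60 − 30 = 30, 120 − 60 = 60 (and 60 again to day 240), then 120 and 180 days. If the restart day is spread evenly between visits (an assumption; visit windows ignored), a scheduled test falls within the 14 days in about 14/30 = 47%, 14/60 = 23%, 14/120 = 12% and 14/180 = 8% of restarts.
2. *Renewed rise.* No level is given. Read literally, a move from 0.8 to 1.2 × ULN after restart means a permanent stop. Yet 1.2 × ULN is below 3 × ULN, hence Grade 0–1, where the same table continues treatment on schedule.
3. *28-day footnote.* In the text as extracted, its marker appears only on the Grade 0–1 row.

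**The case against.** The strongest reply is that Table 2 is the specific guidance and so overrides a general sentence worded only as a recommendation. That is a reasonable reading, but the protocol does not state it. The general rule names Table 2 as its own elaboration, which suggests that the two should agree. The first conflict stands.

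Several stronger readings are tempting, and the documents do not support them.

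- A reader might infer that the protocol authorises rechallenge after a discontinuation criterion. It does not say so. Restart is permitted after interruption, and elsewhere discontinuation leads to an end-of-treatment visit and long-term follow-up (Sections 7.4 and 7.5). For related DILI the Summary says the stop is permanent. What remains is an open question, widest for a patient who meets a laboratory criterion without a DILI attribution.
- A reader might say that a patient at 10 × ULN faces four rival instructions. He falls under the discontinuation list in his own cell. The discretion to interrupt or reduce fits patients who meet no criterion.
- A reader might infer that an untested patient satisfies the 2-week condition. A requirement that values have not increased presupposes a measurement. The gap is that no test is specified.
- The visit intervals of 30 to 180 days are maximum waits for a scheduled test. Restart can fall on any day, and an investigator may test sooner.

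On the smaller points, the word again in the renewed-rise rule may refer back to the size of the first rise. A footnote marker may also have been lost in extraction. Both are weaker evidence than the main conflict.

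**Conclusion.** The hepatic rules are inconsistent as written. For a related Grade 3–4 ALT/AST rise that meets no listed criterion and is not judged DILI, interruption is recommended in one place and optional in another, with two different recovery levels. For a patient who meets a criterion, the document fixes neither whether the stop is permanent nor whether the restart row applies. The first conclusion rests on Grade 3 starting below the 8 × ULN criterion; the second needs no assumption.

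The documents give no rate of transaminase rises, so any count of affected patients would rest on an invented frequency, and none is offered. The rules apply to both blinded arms. At this amendment about 115 of 300 patients were enrolled, so 300 − 115 = 185 (62%) were still to come.

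A reader might infer damage to the primary result. That does not follow: efficacy is analysed by intention to treat, and the double blind limits any difference between arms in how sites apply the text. The consequence is avoidable inconsistency in hepatic safety management and in discontinuation and exposure data between sites.

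**What to change.** Reconcile the Protocol Summary (Dose modification: general requirements and item 2), the general requirements in Section 5.5, the text of Section 5.5.2, and Table 2 with its footnote. The reconciled text should be consistent on:

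1. which rule governs a related Grade 3–4 ALT/AST increase, and at what recovery level treatment may resume;
2. whether a stop under the listed criteria is permanent, and whether those criteria stand alone or only define DILI;
3. whether the restart row applies to patients who met a criterion;
4. how the 2-week condition is verified;
5. what counts as a renewed rise;
6. which rows the 28-day footnote covers.

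The sponsor's medical and safety leads decide the content; no clinical rule is proposed here. The cost is a wording change to one table and the matching paragraphs at the next amendment, plus a memo to sites. Sample size, event target and analyses do not change. Any extra liver test would depend on what the sponsor decides under item 4 and would concern only patients who restart.
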